affected by Lovastatin. Second, the CANTAB has evolved from animal behavior paradigms to facilitate cross-species studies of cognition. As such, it has strong theoretical underpinnings. Third, it has been designed with a neural systems approach in mind, being extensively validated in patients with damage in specific areas of the brain. Fourth, it has extensive functional neuroimaging data available, outlining the neural substrates involved in many of the subtests, providing a useful confirmation of the neuroanatomical basis of the tests. Fifth, the tests are entirely computerized, enabling automatic recording of response accuracy and latencies via a touch-screen apparatus. This increases the consistency of data collection between sites. In addition, there are five equivalent forms available, minimizing retest practice effects. Subtests from the CANTAB start at a simple level and gradually increase in difficulty. Finally, research suggests that computerized batteries, in particular the CANTAB, are sensitive to subtle neurocognitive changes and may be better able to detect subtle cognitive dysfunction and changes over time than traditional paper-and-pencil neuropsychological measures (Bedard et al., 2004; Froestl, Gallagher, Jenkins, Madrid, Melcher et al., 2004; Makdissi, Collie, Maruff, Darby, Bush et al., 2001; Nestor, Scheltens & Hodges, 2004).

In this study, the primary outcome measures have been selected based on the effects of Lovastatin in murine models of NF1 and the cognitive functions that are frequently impaired in children with NF1. Therefore, the primary outcome measures assess visual spatial learning and sustained attention. Visual spatial learning will be assessed using the Paired Associate Learning (PAL) subtest from the CANTAB (see Section 5.1.4.1). Preliminary findings indicate that 46% (13/28) of children with NF1 performance on the PAL is impaired (>1SD below normative mean; Payne, Barton & North, unpublished data). Sustained attention will be assessed using the Score! subtest from the Test of Everyday Attention for Children (TEA-Ch). Previous findings indicate that 63% (50/80) of children with NF1 have impaired performance (>1SD below normative mean) on the Score! subtest (Hyman et al., 2005).

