5.1.4.1 Primary Outcome Measures

The effect of Lovastatin on cognitive functioning in children with NF1 has not been examined. Evidence from a murine model of NF1 suggests Lovastatin improves visual spatial learning and memory, and attention. As such, the following primary outcome measures are:

- Visual Spatial Learning and Memory

*CANTAB Paired Associate Learning (PAL)

PAL is a measure of arbitrary visuospatial associations. It involves the randomized „opening“ of six boxes that are displayed on the screen, each revealing a different pattern. Immediately after presentation of the six patterns, each item reappears in the central box in random order and the participant has to indicate where each item was first seen. Measures include the number of patterns placed correctly on the first trial and the number of repeat presentations needed to learn all the associations correctly. Administration time for this measure is approximately 10 minutes.

- Attention

*Score! Subtest from the Test of Everyday Attention for Children (TEA-Ch: Manly, Robertson, Anderson & Nimmo-Smith, 1999).

The TEA-Ch is a normed and standardized multi-subtest battery that assesses various aspects of attentional function in children aged between 6 years and 15 years 11 months. The Score! subtest requires children to keep count of sounds they hear on a tape. This task does little to „grab“ the child's attention and is a measure of their ability to self-sustain his or her own attention. Previous findings indicate that approximately 63% of children with NF1 are impaired on Score! (Hyman et al., 2005). There are two alternate forms for this subtest and it takes approximately 8 minutes to complete.

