The CGA is an optional computerized clinical outcome measure that will be performed after completion of all secondary outcome measures. It is a virtual environment task that has been developed as a “Human Morris Water Maze” (Astur et al., 2002; Kallai, Makany, Karadi & Jacobs, 2005). The task requires children to use a joystick controller to navigate a circular “arena” to locate an invisible target hidden on the floor. The walls of the arena contain cues, such as windows that remain in place. The fixed target must be located in subsequent trials, each time starting from a new location. This test takes 10-15 minutes to administer and will only be conducted at the following sites: The Children’s Hospital at Westmead, Children’s Hospital Boston and Children’s National Medical Center.

In addition to these measures, Motor Screening (MOT) from the CANTAB will also be administered. MOT is a simple pointing task that measures psychomotor speed and introduces the participant to the touch-screen apparatus, ensuring they can touch the screen accurately, and can hear, understand and follow instructions. The mean latency to touch a cross is measured. MOT takes approximately 5 minutes to administer.

All primary measures will be administered at screening. The length of time required for the child to complete the remainder of the baseline neuropsychological assessment is estimated to be 128 minutes (98 minutes testing and 30 minutes to complete self-report questionnaires). It is estimated that parent questionnaires will take 55 minutes to complete (see Appendix 5). All neuropsychological assessments that will be used in this study are published tests that have normative data that is both reliable and valid for the age range in this study. These tests are all extensively used in clinical and/or research settings. All tests have standardized instructions for administration ensuring there will be no site variation in administration.

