To minimize any test-retest effects for neuropsychological outcome measures, alternate forms (indicated by „*“ in the above sections 5.1.4.1 and 5.1.4.2) will be used where possible, to minimize potential practice effects. Furthermore, the use of a placebo group will allow us to identify any potential practice effects and distinguish whether any changes in the treatment group are larger than those accounted by practice effects i.e. a treatment effect. In addition, statistical analysis of the data will be conducted to account for confounding variables such as practice effects (see Section 8).

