5.1.5 Randomization

Following a successful screening period, the participant will be randomized to one of the two treatment groups: Lovastatin or placebo. Randomization will be implemented by the Data Coordinating Center for this trial utilizing a permuted blocks approach.

Randomization will be stratified by clinical site, to ensure adequate balance between the treatment groups, overall and at each site. Password protection will be implemented to ensure that only certified clinical center personnel are allowed to randomize patients and access the database. At the time of randomization, each participant will be assigned a unique medication kit identification number that will be used throughout the duration of the study.

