5.4 Follow-up

To determine any carry-over effects in the present study, a follow-up assessment will be conducted 8 weeks (± 7 days) post cessation of treatment. As treatment status will be blinded, all participants will be re-administered all outcome measures and laboratory tests (excluding pregnancy test) at follow-up. While no existing data exist on the carry-over effects of Lovastatin, in patients with cancer who were given high dosages of Lovastatin (2-45mg/kg/day)

approximately 30 days after the cessation of Lovastatin, cholesterol levels returned back to normal levels (Thibault et al., 1996).

All study personnel that have responsibility for direct participant related activities will be intensively trained in the relevant specific procedures before contact with participants, which includes providing informed consent/assent, family/child interviews, the administration and scoring of tests, maintenance of confidentiality, data collection and handling, and procedures for handling difficulties that might arise during the study. All study personnel who have direct contact with study participants or their data, will sign a confidentiality form, indicating their understanding of appropriate procedures for maintaining participant confidentiality. Doctoral-level neuropsychology staff and physicians will provide the relevant training and ongoing supervision of all study personnel.

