9.3 Potential Biases and Problems

Challenges may exist in recruiting participants. The Recruitment section of the proposal details participant availability and recruitment measures for the clinical trial. At recruitment, the side effects of the medication, as well as its use in children with NF1 (Phase I), will be reviewed with parents. The system for monitoring side effects will also be discussed. Parents and children will have the opportunity to ask questions regarding use of the medication and will be able to withdraw from the study at any time.

Participants will be stratified to study medication by clinical site to minimize systematic differences in important or unknown confounders between the groups. The requirement for multiple visits may result in some attrition in the sample due to difficulties keeping each of the scheduled appointments. We have included a 10% attrition rate in the calculation of a sample size. To assist in the retention of participants, we will have regular contact with participants throughout the entire study. The investigators, study coordinator, and research assistant will work closely with the families to facilitate their return and maximize participation. All participants will be required to attend scheduled visits. This will allow us to monitor any side effects and may also indirectly assist in maintaining treatment compliance.

Lovastatin has been shown to be safe and effective in a pediatric population for treatment of familial heFH. Although unexpected adverse events may occur, frequent monitoring as well as phone contact with participants and their families will be done throughout the study.

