7.0 Statistics

Determination of sample size: No data exist on the effects of Lovastatin in children with NF1. A clinical and meaningful difference for primary efficacy measures is defined as an effect size of one half of a standard deviation, which is classified as a treatment effect of medium magnitude (Cohen, 1988). A sample size of 64 participants per treatment group (128 total) will be sufficient to detect an effect size of half a standard deviation at the two-sided 0.05 significance level with power of 0.80 (Peat, Mellis, Williams & Xuan, 2001). To allow for a 10% dropout rate prior to the 16-week point, a total of 142 participants will be enrolled.

Interim analyses: Interim analyses will be done under the purview of the DSMB, which will set the content and frequency of analyses. We will propose a Charter containing a data monitoring plan that will include stopping guidelines. We expect these to be the Lan DeMets modifications of the O'Brien Fleming boundaries (Lan & DeMets, 1983; O'Brien & Fleming, 1979)). It is expected that the DSMB will review this charter during its first meeting.

Data analysis: Demographic and baseline characteristics will be summarized for each group using descriptive statistics. Intention-to-treat analyses will be conducted for the primary outcomes measures. An intention-to-treat analysis provides an unbiased, conservative and consistent estimate of a treatment effect (Heritier, Gebiski & Keech, 2003).

Analyzing change scores from baseline to post-treatment does not control for baseline imbalance because of the regression to the mean (Vickers & Altman, 2001). Also, with changes scores, if the treatment is effective, the statistical significance of the treatment effect will depend upon the correlation between baseline and follow-up scores. Therefore, to determine whether there has been a significant change from baseline to post-treatment, primary and secondary outcomes will be analyzed using ANCOVA, which is a better approach than analyzing change scores with independent t-tests (Vickers & Altman, 2001).

In addition, at an individual case level to determine whether test-retest change scores from baseline to post-treatment are reliable and clinically meaningful, standardized regression based

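### Randomisation is stratified by clinical site but the ANCOVA in section 7.0 names no site term; without one the model standard error is somewhat too large and the test slightly conservative

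*SAP*

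**What the plan says.** Protocol 5.1.5 describes a permuted-blocks scheme and states: "Randomization will be stratified by clinical site, to ensure adequate balance between the treatment groups, overall and at each site". Protocol 9.3 gives the reason: "Participants will be stratified to study medication by clinical site to minimize systematic differences in important or unknown confounders between the groups". Site is the only stratification factor named.

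Section 7.0, with the same text in the protocol and the SAP, says that "primary and secondary outcomes will be analyzed using ANCOVA, which is a better approach than analyzing change scores with independent t-tests". It lists no covariates. Its argument against change scores makes it clear that the baseline score is to be adjusted for. Site does not appear as a fixed effect, a random effect or a stratified analysis. The optional linear mixed models later in 7.0 do not mention it either.

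The only other statement on adjustment is in Protocol 5.1.4.2, which promises that "statistical analysis of the data will be conducted to account for confounding variables such as practice effects". That is general, does not name site, and refers the reader to Section 8, which is Data Management and contains no model.

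**The concern.** Blocking within site keeps the arms nearly balanced at each site, so differences between sites largely cancel out of the treatment contrast. A model that omits site does not know this. It leaves the between-site variation in the residual and reports a standard error larger than the design warrants, whenever site predicts the week-16 score beyond what the baseline score already explains.

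At stake is some of the precision that stratification was meant to provide, and confidence intervals slightly wider than they need be. There is also a small matter of prespecification. With and without site are both defensible models and section 7.0 allows either, so the choice for the primary test should be made before unblinding.

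**Working it through.** **Inputs from the documents (section 7.0).** Effect 0.5 SD, two-sided 0.05, power 0.80, 64 per arm (128), 10% dropout, 142 enrolled. Not given: site variance, correlation between baseline and week-16 scores, block size. The number of sites is not visible in the public text. These four are assumed below and varied where they matter.

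**1. The plan's own figure.** A two-sample t-test with 64 per arm and 0.5 SD has power 0.801. 128 / 0.9 = 142.2, against 142 stated. The sample size reproduces, and it takes no credit for baseline adjustment.

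**2. Standard error with and without site, stable site effects.** Set the week-16 variance to 1. Let s be the share of it due to site and r the correlation of baseline and week-16 scores within site. Assume balance within site and many sites.

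- Residual variance with site: (1 − s)(1 − r²).
- Residual variance without site, when the site effect is the same at both visits: 1 − [s + (1 − s)r]².
- The ratio simplifies to 1 + s(1 − r)/(1 + r). The standard-error excess is its square root minus 1.

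Example, s = 0.10 and r = 0.5: 1 − 0.55² = 0.6975; 0.9 × 0.75 = 0.675; √(0.6975/0.675) = 1.017.

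| Site share s | r = 0.3 | r = 0.5 | r = 0.7 |
|---|---|---|---|
| 0 | 0% | 0% | 0% |
| 0.02 | 0.5% | 0.3% | 0.2% |
| 0.05 | 1.3% | 0.8% | 0.4% |
| 0.10 | 2.7% | 1.7% | 0.9% |

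A simulation with 8 sites of 16, blocks of four and s = 0.10 gives mean model standard errors of 0.1475 without site and 0.1455 with it at r = 0.5 (1.4%), and 0.1210 and 0.1200 at r = 0.7 (0.8%). Power for 0.5 SD is 0.923 without site and 0.926 with it at r = 0.5, and 0.987 and 0.988 at r = 0.7.

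**3. Site effects that differ between visits (s = 0.10).**

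- Correlated 0.8 across visits: 1 − [0.8s + (1 − s)r]² gives 0.7191/0.675 at r = 0.5 and 0.4959/0.459 at r = 0.7, an excess of 3.2% and 3.9%.
- Present at week 16 only: 1 − (1 − s)r² gives 0.775/0.675 and 0.559/0.459, an excess of 7.2% and 10.4%.
- Independent at the two visits: 1 − [(1 − s)r]² gives 0.7975/0.675 and 0.6031/0.459, an excess of 8.7% and 14.6%.

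In the 8-site simulation of the week-16-only case, type I error is 0.039 without site and 0.050 with it at r = 0.5, and 0.032 and 0.048 at r = 0.7. Power is 0.908 and 0.928 at r = 0.5, and 0.978 and 0.988 at r = 0.7.

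**4. Planned power.** Without site, the residual variance is 1 minus the squared overall correlation of baseline with week 16, so it cannot exceed 1, the variance behind the plan's 64 per arm. The standard error is therefore at most about √(2/64) = 0.177, apart from one degree of freedom for baseline. At r = 0.3, simulated power without site was 0.83 to 0.86.

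**5. Cost of adding site when it has no effect.** With 142 randomised at 8 sites and 10% random dropout, power without and with site is 0.896 and 0.892 (r = 0.5), and 0.973 and 0.971 (r = 0.7). With unequal sites (40, 28, 20, 14, 10, 8, 5, 3) it is 0.901 and 0.899, and 0.974 and 0.974. Monte Carlo error on power is 0.004 or less.

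**The case against.** The strongest reply is that this is silence with little consequence. An ANCOVA with site is fully consistent with section 7.0, which does not even list baseline explicitly. The documents also suggest a small site effect. Protocol 5.1.4.2 states: "All tests have standardized instructions for administration ensuring there will be no site variation in administration". Of the computerised battery, Protocol 1.9 says: "This increases the consistency of data collection between sites". For the other primary measure, Protocol 5.1.4.1 notes: "The Score! subtest requires children to keep count of sounds they hear on a tape". Under Protocol 5.4, staff "will be intensively trained in the relevant specific procedures before contact with participants". The site psychologist also gives the screening tests (Protocol 5.1.1), so a stable tester effect would largely be absorbed by the baseline score. With no site effect, adding site costs a little power, and that cost is about as large as the gain in the stable case.

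Most of this stands, and it is why the point is minor. It does not remove the mismatch between design and analysis. Standardised testing limits tester variation but not differences in the children recruited, and Protocol 9.3 itself treats site as a possible source of confounding.

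A reader might infer more than the documents support. Omitting site does not bias the estimate, because arms are randomised within site. It does not inflate type I error; the error runs the other way. It does not leave the trial underpowered (step 4). Nor does the plan exclude site; it leaves it open.

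**Conclusion.** The point holds as a minor gap. Site is the only stratification factor and the ANCOVA does not name it. Run with the baseline score alone, the analysis is valid and slightly conservative.

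No single figure for the loss can be derived from the documents. With stable site effects it runs from nil to 1.7% of the standard error for site shares up to 0.10 at within-site correlation 0.5. It is less at 0.7 and up to 2.7% at 0.3. The lower end is the more plausible, given the standardised testing. The 7% to 15% figures need a site share of 0.10 together with site effects that are unrelated at the two visits or appear only at week 16. Those are unlikely here, and they show sensitivity rather than a bound. The power figures apply only to the cells simulated.

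**What to change.** State in section 7.0 of the protocol and SAP that the primary and secondary week-16 analyses are ANCOVA of the week-16 score on randomised arm, with the baseline score of the same measure and clinical site as covariates. If very small sites are to be pooled, write the rule down before unblinding. The documents offer no basis for a particular threshold, so the sponsor should set one from the site enrolment numbers.

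The cost is a sentence or two of wording and a few degrees of freedom. If site turns out to have no effect, the power loss was roughly half a point or less in the simulated cells. Sample size, procedures and data collection do not change.

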8.0 Data Management

Data sets will follow all standards as per Data Coordinating Center's guidelines and recommendations. All paper charts, forms, and information associated with this study will be kept in a locked cabinet at the clinical sites. Access to this cabinet is available only to investigators on the study and research assistants. All participant information from this study will be strictly confidential. On entry to the study, participants will be assigned a unique PIN that will be used throughout the study. All data stored in computer systems will be password protected and stored using participant PINs only (see next section for more information regarding database security). Participant names will not be used in any computer databases associated with this project. A list of participant names and coordinating PINs will be kept separately on the password-protected principal investigator's computer. This information will be kept in accordance with the requirements of the Department of Defense.

8.1 Medical Monitor and Data Safety Monitoring Plan

The Data Safety and Monitoring Plan for this study will follow the NIH guidelines. The External Advisory Board (EAB) will serve as external reviewers and advisors to DoD and the Governing Body. The EAB will review and approve the protocol with respect to ethical and safety standards. Its primary responsibility will be to monitor the emerging results of the trial to assess treatment representatives are *ex officio* members of the EAB. The EAB will determine the content and frequency of safety reports it will review and will periodically review interim analyses of data collected for this study.

In addition, the DSMB will protect the integrity of the study by ensuring that recruitment targets can be met within the study timelines. This will be achieved by comparing actual recruitment against planned and by monitoring participant drop-out rates. In the event that the number of accrued patients is less than 20% of the planned value, the DSMB will advise on appropriate remedial action. Possible remedial actions may include, but are not limited to, the extension of the recruitment period, review and amendment of inclusion criteria.

[name] will be the medical monitor for this study. She is a qualified physician and is not associated with this protocol. She will work closely with the Principal Investigator to monitor the participants' treatment while on this study. The medical monitor is required to review all unanticipated problems involving risk to subjects or others, serious adverse events and all subject related deaths associated with the protocol, providing an unbiased written report of the event. At minimum, the medical monitor should comment on the outcomes of the event or problem, and in the case of a serious adverse event or death, comment on the relationship to participation in the study. The medical monitor should also indicate whether she concurs with the details of the report provided by the study investigator. Reports for events determined by either the investigator or the medical monitor to be possibly or definitely related to participation and reports of events resulting in death should be promptly forwarded to the USAMRMC ORP HRPO.

It is expected that summaries of accrual, retention, and adverse events will be disseminated to the clinical centers periodically. To maintain the blind, adverse events will be aggregated across treatment arms.

